1.2.2 Residual Effect Period

Based on an effective half-life of 33 h the Residual Effect Period (REP) of BI 1358894 is 11 days. This is the period after the last dose with measurable drug levels and/or pharmacodynamic effects is still likely to be present.

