1.2 DRUG PROFILE

1.2.1 BI 1358894

For a detailed description of the BI 1358894 profile, please refer to the current Investigator's Brochure (IB) [\[c10354149\]](#).

Pharmacokinetics in Humans

Human PK data are currently available from the FIM study 1402-0001, which consisted of an SRD part (tested doses: 3 mg – 200 mg BI 1358894) and a food effect part (tested doses: 50 mg and 100 mg BI 1358894 under fasted and fed conditions) [report in preparation].

Following oral administration of film-coated tablets in fasted state BI 1358894 reached maximum plasma concentrations after 1 to 5 hours. Thereafter BI 1358894 plasma concentrations declined in a multiphasic fashion implying multi-compartmental distribution and exhibited a long terminal phase, which seems to be dose-independent.

C_{max} , AUC_{0-72} and $AUC_{0-\infty}$ of BI 1358894 increased in a dose dependent way. Preliminary statistical evaluation showed that the increase in C_{max} and AUC_{0-72} was less than dose proportional. $AUC_{0-\infty}$ increased slightly less than dose proportional when given without food.

Also the food effect was dependent on the administered dose. While the exposure of BI 1358894 increased by factor 1.6 for the 50 mg dose, a food effect of factor 2.5 was observed for the 100 mg dose.

After completion of the food effect assessment, a dose of 200 mg BI 1358894 has been given after a high-calorie, high-fat meal in the SRD part of 1402-0001. Compared to the cohort receiving 200 mg under fasted conditions, food increased exposure by about 2.4-fold (exposure of 200 mg BI 1358894, fed conditions: $C_{max} = 857 \text{ nM}$, $AUC_{0-24} = 11640 \text{ nM} \cdot \text{h}$).

Based on PK data of previous dose groups (DGs) in the 200 mg fed DG PK blood sampling was extended to 672 h. Sampling from 240 h to 672 h revealed another phase with low plasma concentrations and long terminal half-life of about 200 h. The proportion of AUC beyond 192 h is less than 20% of total AUC. Hence, it is not expected that this phase markedly contributes to accumulation or steady state attainment.

Preliminary PK data from the ongoing MRD study 1402-0002 support this observation. In the first dose groups (10 mg and 25 mg), an accumulation ratio (based on AUC_{0-24}) of 2.5 was observed. Steady state seems to be achieved after about a week. Both accumulation ratio and approximation of steady state attainment are in line with an effective half-life of ~33h.

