2.1.2 Primary endpoints

Part 1

The following pharmacokinetic parameters will be determined for BI 1358894:

- $AUC_{0-\infty}$ (area under the concentration-time curve of the analyte over the time interval from 0 to infinity after i.v. administration) for (C-14) BI 1358894 i.v.
- $AUC_{0-\infty}$ (area under the concentration-time curve of the analyte over the time interval from 0 to infinity after oral administration) for BI 1358894 p.o.

Part 2

The following pharmacokinetic parameter will be determined for BI 1358894:

- AUC_{0-312} (area under the concentration-time curve of the analyte in plasma over the time interval from 0 to 312 h)

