6. INVESTIGATIONAL PLAN

6.1 VISIT SCHEDULE

Exact times of measurements outside the permitted time windows will be documented. The acceptable time windows for screening and the end of trial examination are provided in the [Flow Chart](#).

Study measurements and assessments scheduled to occur 'before' trial medication administration on Day 1 of each treatment period are to be performed and completed within a 2 h-period prior to the trial drug administration.

The acceptable deviation from the scheduled time for vital signs, ECG, and laboratory tests will be \pm 10 min for the first 4 h following the trial drug administration (on Day 1 of each treatment period) and \pm 30 min thereafter until discharge on Day 5. During the ambulatory visits, the acceptable deviation from the scheduled time for vital signs, ECG, and laboratory tests will be \pm 120 min.

If scheduled in the [Flow Chart](#) at the same time as a meal, blood sampling, vital signs, and 12-lead ECG recordings have to be done first. Furthermore, if several measurements including venepuncture are scheduled for the same time, venepuncture should be the last of the measurements due to its inconvenience to the subject and possible influence on physiological parameters.

For planned blood sampling times, refer to the [Flow Chart](#). While these nominal times should be adhered to as closely as possible, the actual sampling times will be recorded and used for the determination of pharmacokinetic parameters.

If a subject misses an appointment, it will be rescheduled if possible. The relevance of measurements outside the permitted time windows will be assessed no later than at the Report Planning Meeting.

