10.2 COVID-19 RELATED ASSESSMENT AND RISK MITIGATION

This section contains a risk assessment for study 1402-0016 with BI 1358894 due to the circumstances created by the coronavirus disease-19 (COVID-19) pandemic. In addition, the document summarizes the mitigation approaches to be followed to minimize the risk of spreading severe acute respiratory syndrome coronavirus 2 (SARS CoV-2).

Risk Assessment

BI 1358894 is a TRPC4/5 inhibitor in development for treatment of Major Depressive Disorder and for the treatment of Borderline Personality Disorder (BoPD). It is expected that treatment with BI 1358894 has the potential to improve affective symptoms and emotion control, especially in patients with MDD who inadequately respond to the current standard of care (SSRI; SNRI) and in patients with BoPD, where no approved drug treatment is currently available

Relevant information on the product

BI 1358894 is a highly potent and selective TRPC4/5 Inhibitor (transient receptor potential cation channel, subfamily C, members 4 and 5). It has the potential to address core symptoms of MDD and BoPD as it targets TRPC4/5 ion channels. TRPC4 and TRPC5 are highly expressed in pyramidal neurons of the amygdala in the frontal cortex, hippocampus, and hypothalamus, brain areas that are involved in circuits contributing to emotional control. BI 1358894 is thought to decrease neuronal excitability leading to normalization of the activation state of limbic circuits, which are known to be important for emotional control.

BI 1358894 is characterised by high bioavailability after oral intake, moderate volume of distribution, low clearance and long terminal half-life. Excretion occurs almost exclusively via faeces. After administration of BI 1358894 tablets, maximum plasma concentrations of BI 1358894 occurred around 1 to 5 hours after dosing. The terminal half-life was 41 to 52 hours for blood. Steady state was reached after 11 to 14 days of BI 1358894 dosing.

Currently, repeat dose toxicity studies up to 13 weeks revealed toxicologically relevant effects on the skin (mice), Harderian glands (mice), hepatic function (mice), the vascular system (rats), male genital tract (rats), the Central Nervous System (CNS) function (dogs), and the digestive tract, renal function, and white blood cell parameters (mice, rats and dogs).

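### Is the 11-day residual effect period wrongly based on an accumulation half-life, so that late adverse events and the Day 14 laboratory sample drop out of the safety summaries?

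*Protocol*

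**What the plan says.** Protocol 1.2.2 gives an REP of 11 days on the basis of a 33 h effective half-life and explains it as follows: "This is the period after the last dose with measurable drug levels and/or pharmacodynamic effects is still likely to be present". It states no multiplier.

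Protocol 1.2.1 gives the origin of the 33 h, from the first dose groups of the multiple-dose trial: "Both accumulation ratio and approximation of steady state attainment are in line with an effective half-life of ~33h". For the 200 mg fed group it reports: "Sampling from 240 h to 672 h revealed another phase with low plasma concentrations and long terminal half-life of about 200 h". It then sets that phase aside: "Hence, it is not expected that this phase markedly contributes to accumulation or steady state attainment". On steady state it says: "Steady state seems to be achieved after about a week". Protocol 10.2 has different figures: "The terminal half-life was 41 to 52 hours for blood. Steady state was reached after 11 to 14 days of BI 1358894 dosing".

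SAP 6.1 (Table 6.1: 1) applies the REP as 11 x 24 h, counted from dosing in Part 2 and from the end of the infusion in Part 1. The named adverse event displays cover on-treatment phases only. Laboratory values count as on-treatment by the same phases, and the shift table in SAP 7.8.2 runs from baseline to the final on-treatment value.

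Protocol 5.2.3 schedules safety laboratory tests on Days 11 and 14 of every period. The Part 2 primary endpoint in Protocol 2.1.2 is the "area under the concentration-time curve of the analyte in plasma over the time interval from 0 to 312 h".

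**The concern.** An effective half-life recovered from an accumulation ratio describes how drug builds up on repeated dosing. It does not say how long a single dose stays above the assay limit. The protocol dismisses the 200 h phase only for accumulation and steady state, and is silent on measurability. The trial itself samples 48 h beyond the REP (312 - 264). The half-lives and times to steady state in Protocol 1.2.1 and 10.2 also differ.

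If the cut-off came too early, a drug-related event with late onset would be counted as follow-up and would be missing from the main tables, including the total over all on-treatment phases. A laboratory change first seen on Day 14, a planned safety sample in all three periods, could not appear in the shift table. The SAP also does not say outright whether Day 14 enters the laboratory statistics by time point.

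**Working it through.** **Inputs.** Effective half-life 33 h and REP 11 days (Protocol 1.2.2). Accumulation ratio 2.5 on AUC over 24 h (Protocol 1.2.1). Infusion from 5 h to 5.25 h after the tablet (Protocol 3.1 and 4.1.1). Day 11 = 240 h and Day 14 = 312 h (Flow Charts). Ambulatory visit window (Protocol 6.1): "During the ambulatory visits, the acceptable deviation from the scheduled time for vital signs, ECG, and laboratory tests will be" plus or minus 120 min. At least 17 days = 408 h between doses (Protocol 3.1).

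**The plan's own figures.**
- Half-life implied by accumulation: 24 x ln 2 / ln(2.5/1.5) = 32.6 h, which matches the 33 h.
- REP: 8 x 33 h = 264 h = 11 days exactly. The multiplier of 8 is inferred.

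**Where the cut-off falls.**
- Part 2: 264 h after dosing. Part 1: 5.25 + 264 = 269.25 h after the tablet.
- Day 11: 238 to 242 h, inside both limits, so it is the last scheduled on-treatment sample.
- Day 14: 310 to 314 h. That is 46 to 50 h past the Part 2 limit and 40.75 to 44.75 h past the Part 1 limit.
- Follow-up share of the minimum interval: (408 - 264)/408 = 35.3% in Part 2 and (408 - 269.25)/408 = 34.0% in Part 1.

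**Is 264 h short by the protocol's other half-lives?**
- 264/41 = 6.4 half-lives and 264/52 = 5.1. Protocol 5.2.6.1.6 mentions 5 half-lives as an example when judging causality, and both figures exceed it.
- 264/200 = 1.3, but that phase is described as low concentrations and was seen at 200 mg fed. If exposure is proportional to dose, 100 mg fed gives half of it, and 100 mg fasted gives 1/(2 x 2.4) = 0.21 of it, using the 2.4-fold food effect in Protocol 1.2.1.
- On a 200 h half-life, the 264 h level is 2^(408/200) = 4.1 times the 672 h level. Scaled to 100 mg, that is about 2.1 times the 200 mg fed 672 h level when fed and about 0.86 times when fasted. No assay limit or 672 h value is given, so this does not settle whether drug is measurable.

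**What a longer REP would do.** The REP also decides which values are off-treatment and so may serve as baseline (SAP 6.7). The next period's Day -1 sample is due 408 - 22 = 386 h after the previous dose at the minimum interval. Applying the same multiplier of 8, for sensitivity only:
- 41 h gives 328 h, which would take in Day 14.
- 52 h gives 416 h, past both the Day -1 sample and the next dose.
- 200 h gives 1600 h.

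At the two larger values, phases would overlap at the minimum interval and the Day -1 sample would no longer qualify as baseline.

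**The case for a change.** The strongest case for a change is that Day 14 is a scheduled safety sample, that the protocol asks for timely detection of liver laboratory changes, and that Protocol 7.3.4 lets the SAP define further intervals. One table of adverse events from dose to next dose and one shift table through Day 14 would need no new data.

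The mismatch in the rationale stands. So does the fact that the shift table cannot show Day 14. The rest is weaker:

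- The definition offers measurable levels and/or pharmacodynamic effects, and asks only whether they are likely. It is not a pure test of measurability.
- The differing figures have partly different sources. The 41 to 52 h is quoted for blood, while Protocol 1.2.1 deals with plasma. The one-week steady state is preliminary, from 10 and 25 mg, and has no direct bearing on a single-dose cut-off.
- Sampling to 312 h does not show that levels at 312 h are quantifiable.
- Protocol 7.3.4 assigns post-REP events to follow-up in advance. Events are collected to the end of trial (Protocol 5.2.6.2.1), and all individual values are listed (SAP 7). Serious events, events of special interest and other significant events are listed separately (Protocol 7.3.4).
- SAP 7.8.2 gives laboratory statistics by planned time point, and nothing there limits them to on-treatment values. An analyst would include Day 14 as a planned time.

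The extra tables also have costs. An event table from dose to next dose has unequal windows: at least 408 h between doses, and 408 to 528 h from the last dose to the Day 52 to 57 visit if doses fall on Days 1, 18 and 35. It also counts more background events. A shift table to the worst scheduled value answers a different question from one to the final value, picks up transient deviations, and sits badly with the SAP's rule that unscheduled repeats join the preceding planned time point. Such tables are allowed but optional.

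**Conclusion.** No change to the plan is needed. The reason given for 11 days is terse and does not address measurability or the late phase. Writing down the multiplier and reconciling Protocol 1.2.1, 1.2.2 and 10.2 would tidy the text without altering any analysis. The documents do not show that the REP is too short at 100 mg, and no rule in the SAP is shown to give a wrong result.

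The practical effect is confined to summary displays. Events starting after 264 h or 269.25 h move to follow-up. At most 12 x 3 = 36 scheduled Day 14 laboratory panels, if 12 subjects complete all periods, cannot supply the final on-treatment value. All remain in the listings, which can be read directly at this sample size.

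The cut-off is a fair trade-off: it follows each subject for 11 days and still leaves an off-treatment baseline before the next dose. This conclusion assumes that the listings are reviewed with the tables and that Day 14 is reported as an ordinary planned time point. It would need another look if concentrations at 100 mg after 264 h proved clearly quantifiable and relevant to safety; the documents give no figures from which to judge that.

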1.3 RATIONALE FOR PERFORMING THE TRIAL

This trial is intended to examine the absolute oral bioavailability of BI 1358894 as tablet formulation for oral administration using an intravenous (i.v.) [C-14] microtracer approach (Part 1) and to investigate the relative bioavailability of the oral suspension (Part 2). The data are considered necessary to further support the understanding of the pharmacokinetics of BI 1358894.

1.4 BENEFIT - RISK ASSESSMENT

Participation in this clinical trial is without any (therapeutic) benefit for healthy subjects. Their participation, however, is of major importance for the development. Subjects are exposed to risks of study procedures and risks related to the exposure to the trial medication.

Procedure-related risks

The use of an indwelling venous catheter or venepuncture for e.g. blood sampling may result in mild bruising, and in rare cases, in transient inflammation of the wall of the vein, or nerve injury, potentially resulting in paraesthesia, reduced sensibility, and/or pain for an indefinite period.

The solvent for the intravenous infusion containing a mixture of labelled and unlabelled BI 1358894 is isotonic sodium chloride solution (0.9%). Therefore, in case of inadvertent paravenous drug administration apart from local swelling no tissue damage is expected.

The total volume of blood withdrawn per subject during the entire study will not exceed the volume of a normal blood donation (500 mL). No health-related risk to healthy subjects is expected from withdrawal of this volume of blood.

Drug-related risks and safety measures

The single dose administration of up to 200 mg BI 1358894 under fasted and fed conditions has been well tolerated by healthy subjects in the single rising dose trial [[c28907328](#)] as well as the single dose administration of 100 mg under fasted and fed administration in the relative bioavailability trial 1402-0010 [[c28907328](#)]. Therefore no undue risk is expected from the single dose administration of 100 mg BI 1358894 to healthy subjects planned for this trial. A more detailed description of BI 1358894 tolerability in healthy subjects can be found in Section [1.2.1](#).

Drug-induced liver injury (DILI):

Although rare, a potential for drug-induced liver injury (DILI) is under constant surveillance by sponsors and regulators. Therefore, this trial requires timely detection, evaluation, and follow-up of laboratory alterations in selected liver laboratory parameters to ensure subjects' safety; see also Section [5.2.6.1.4](#), adverse events of special interest.

Proprietary confidential information © 2020 Boehringer Ingelheim International GmbH or one or more of its affiliated companies

Administration of ^{14}C -labelled BI 1358894

BI 1358894 is labelled with the isotope [^{14}C] which is necessary for the purposes of this microtracer trial to distinguish the i.v. drug from the unlabelled oral drug. The radioactive dose per infusion has been calculated to be 0.039 MBq which does not exceed the threshold of 0.1 MBq, and thus falls into the ICRP 1 category (negligible radio burden) that is considered acceptable.

Overall assessment

In a previous trial, single oral doses up to 200 mg BI 1358894 administered in fed and fasted state as tablets were safe and well-tolerated. In the current trial, single oral dose of 100 mg BI 1358894 will be administered to healthy male subjects which will give an appropriate safety margin to the highest dose safely tested in the SRD (1402-0001). Each participant will be receiving a single i.v. infusion of a microtracer [^{14}C] BI 1358894 containing a radioactive dose <0.1 mSv (ICRP 1 category, negligible radioburden).

The trial design is optimized to collect as much relevant information as possible on the pharmacokinetics of BI 1358894 without exposing participating volunteers to undue risk. However, there is always the potential of serious adverse events (SAEs) occurring with intake of trial medication. Risks to subjects will be minimized and addressed by eligibility criteria, safety laboratory examinations, ECG and vital sign measurements, in-house observation periods and verbal communication concerning AEs.

If the investigator should have any clinical concern, the safety of the subjects will be of paramount importance. The investigator has the discretion to remove subjects from the study should there be any safety concerns or if the subject's wellbeing is at jeopardy.

The risk associated with the expected maximal radiation burden falls in ICRP category 1 with minor level risk. This is considered to be acceptable.

The risk to participating subjects is minimized and justified when compared to the potential benefit that a successful clinical development of BI 1358894 could provide to the treatment of major depressive disorder and borderline personality disorder.

2. TRIAL OBJECTIVES AND ENDPOINTS

2.1 MAIN OBJECTIVES, PRIMARY AND SECONDARY ENDPOINTS

2.1.1 Main objectives

Part 1

The main objective of Part 1 of this trial is:

- To investigate the absolute bioavailability of 100 mg of BI 1358894 (Test 1, T1) with an intravenous microdose formulation containing labelled [C-14] BI 1358894 and an unlabelled oral tablet formulation of BI 1358894 in healthy male subjects.

Part 2

The main objective of Part 2 of this trial is:

- To investigate the relative bioavailability of BI 1358894 administered as an oral suspension.

2.1.2 Primary endpoints

Part 1

The following pharmacokinetic parameters will be determined for BI 1358894:

- $AUC_{0-\infty}$ (area under the concentration-time curve of the analyte over the time interval from 0 to infinity after i.v. administration) for (C-14) BI 1358894 i.v.
- $AUC_{0-\infty}$ (area under the concentration-time curve of the analyte over the time interval from 0 to infinity after oral administration) for BI 1358894 p.o.

Part 2

The following pharmacokinetic parameter will be determined for BI 1358894:

- AUC_{0-312} (area under the concentration-time curve of the analyte in plasma over the time interval from 0 to 312 h)

2.1.3 Secondary endpoints

Part 1

The following pharmacokinetic parameter will be determined for BI 1358894:

[figure not shown]
- C_{\max} (maximum measured concentration of the analyte after oral administration)

[figure not shown]
Part 2

The following pharmacokinetic parameters will be determined for BI 1358894:

Proprietary confidential information © 2020 Boehringer Ingelheim International GmbH or one or more of its affiliated companies

- C_{\max} (maximum measured concentration of the analyte after oral administration)
- $AUC_{0-\infty}$ (area under the concentration-time curve of the analyte in plasma over the time interval from 0 extrapolated to infinity after oral administration)

2.2.2.2 Safety and tolerability

Safety and tolerability of BI 1358894 will be assessed based on:

- Adverse events (including clinically relevant findings from the physical examination)
- Safety laboratory tests
- 12-lead ECG
- Vital signs (blood pressure, pulse rate)
- Suicidality assessment (C-SSRS)

Proprietary confidential information © 2020 Boehringer Ingelheim International GmbH or one or more of its affiliated companies

3. DESCRIPTION OF DESIGN AND TRIAL POPULATION

3.1 OVERALL TRIAL DESIGN AND PLAN

Part 1 of the study will be performed as a non-randomised, open-label trial in healthy male subjects in order to investigate the pharmacokinetics and absolute bioavailability of BI 1358894 as an oral tablet co-administered with an i.v. microtracer dose of [C-14]-BI 1358894. The reference treatment in Part 1 (Reference 1 – R1) will be 10 mL intravenous infusion of 100 µg BI 1358894 using a mixture of 90 µg unlabelled and 10 µg [C-14] labelled BI 1358894. The oral treatment (Test 1 – T1) will consist of two 50 mg BI 1358894 tablets administered on Day 1 to subjects in the fasting state. The i.v. infusion will start 5 hours after oral drug administration, i.e. at the time of the expected t_{max} .

This will be followed by Part 2 of the study which will be performed as a randomised, open-label, single-dose, two-period, two-sequence cross-over trial to investigate the relative bioavailability of BI 1358894 administered as an oral suspension. In Part 2, the treatments will consist of a single dose of 100 mg BI 1358894 administered as an oral suspension either in the fasted state (Reference 2 – R2) or in the fed state (Test 2 – T2). In Part 2, the subjects will be randomly allocated to the 2 treatment sequences (T2-R2 or R2-T2).

Part 1 and Part 2 are designed in a fixed sequence.

For details, refer to Section [4.1](#).

There will be a washout period of at least 17 days between the treatments, i.e. the dosing in Part 1 and the dosing in the first treatment period of Part 2, as well as the dosing in the first treatment period of Part 2 and the dosing in the second treatment period of Part 2 are separated by at least 17 days.

An overview of all relevant trial activities is provided in the [Flow Chart](#). For visit schedule and details of trial procedures at selected visits, refer to Sections [6.1](#) and [6.2](#), respectively.

